2.3.2 Benefit assessment

Information gained from this study will support the development of a growth hormone product with clinical advantages over currently available products to children with SGA, TS, NS and ISS.

For most of the participating children the administration of study intervention during the study most likely reduces the treatment burden compared to current available therapy as somapacitan is administered once weekly.

It is expected that many participating treatment naïve children will experience increased height velocity compared to pre-study experience.

Participating children might benefit from the increased attention during the participation of the study which might lead to an increase in treatment adherence.

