8.1.5 Clinical outcome assessments

Clinical outcome assessment (COA) questionnaires should be completed by participants at visits specified in the flowchart (Section [1.2](#)). An overview of COAs relevant for the study is outlined in [Table 8-1](#).

The COAs should only be collected from participants switching to somapacitan from daily GH treatment.

COA questionnaires will be available as paper copies. The investigator or delegated site staff must train the participants in COA questionnaire completion, as applicable.

The investigator must ensure that the COA questionnaires are reviewed and transcribed to the CRF.

Table 8-1 Clinical outcome assessment questionnaires

COA questionnaire	Estimated time to complete the individual questionnaire
Growth Hormone Injection – Child Treatment Burden – Child (GH-INJ-CTB-Child)	3 min
Growth Hormone Patient Preference Questionnaire - Child (GH-PPQ-Child)	3 min

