9.3.6 Other analyses

Other parameters

Table 9-2 Overview of other parameters

Title	Time frame	Unit	Details
Child treatment burden measure: GH-INJ-CTB-Physical ^e	Visit 5	Score ^a	GH-INJ-CTB-Physical score at week 13 (visit 5). GH-INJ-CTB – Physical score is derived as the sum of the 4 items (0=Not at all, 1=A little, 2=Some, 3=A lot, 4=Extreme) normalised to a 0-100-point scale as: Physical (question 1-4): (Sum/16)*100
Child treatment burden measure: GH-INJ-CTB-Emotional Well-being ^e	Visit 5	Score ^a	GH-INJ-CTB-Emotional Well-being score at week 13 (visit 5). GH-INJ-CTB – Emotional Well-being score is derived as the sum of the 4 items (0=Not at all, 1=A little, 2=Some, 3=A lot, 4=Extreme) normalised to a 0-100-point scale as: Emotional Well-being (question 5-10): (Sum/24)*100
Child treatment burden measure: GH-INJ-CTB-Interference ^e	Visit 5	Score ^a	GH-INJ-CTB-Interference score at week 13 (visit 5). GH-INJ-CTB – Interference score is derived as the sum of the 4 items (0=Not at all, 1=A little, 2=Some, 3=A lot, 4=Extreme) normalised to a 0-100-point scale as: Interference: (question 11-14): (Sum/16)*100
Child treatment burden measure:	Visit 5	Score ^a	GH-INJ-CTB-Overall treatment burden score at week 13 (visit 5).

Title	Time frame	Unit	Details
GH-INJ-CTB Overall treatment burden ^e			GH-INJ-CTB – Overall treatment burden score is derived as the mean of the GH-INJ-CTB – Physical score, GH-INJ-CTB - Emotional Well-being score and GH-INJ-CTB – Interference score.
Patient Preference: GH-PPQ-Child ^e	Visit 5	Categorical response	Patient Preference GH-PPQ-Child at week 13 (visit 5) (Previous treatment, Current treatment, No preference).
Near adult height (NAH)	18 months prior to screening to end of treatment	Yes/No	Near adult height (NAH) will be derived. NAH is defined as HV < 2 cm/year calculated over a period of at least 9 months, males have reached a bone age of ≥ 16 years and females has reached a bone age of ≥ 14 years. If bone age is not available, then males have reached a chronological age of ≥ 17 years and females have reached a chronological age of ≥ 15 years. Historical height measurements collected at screening will be included in the derivation.
Change in height SDS at the visit when NAH is reached	From baseline (week 0) to the visit NAH is reached	Score ^b	Derived as the Height SDS value at baseline week 0 subtracted from the Height SDS value at the visit where NAH is reached.

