aNegative score indicates that treatment burden is less compared to baseline.bPositive score indicates that the value is closer to or above the reference population compared to baseline.cNegative values indicate that the values are lower than the reference population.dNegative values indicate that the NAH is below the genetic height potential.eOnly to be collected from participants switching to somapacitan from daily GH treatment.

Height Velocity at visit 9 (week 52), Change in Height SDS from baseline (week 0) to visit 9 (week 52), Change in Height Velocity SDS from baseline (week 0) to visit 9 (week 52), Change in IGF-1 SDS from baseline (week 0) to visit 9 (week 52) and Change in IGFBP-3 SDS from baseline (week 0) to visit 9 (week 52) will be derived as parameters in the same way as the corresponding secondary endpoints at visit 7 (week 26).

The parameters will be summarised for relevant indications, SGA, TS, NS or ISS.

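### Treatment burden (GH-INJ-CTB) is an absolute 0-100 score taken once, at week 13 after the switch, but its footnote interprets it as a change from baseline

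*SAP*

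**What the plan says.** Protocol Section 9.3.6, Table 9-2, lists four GH-INJ-CTB parameters: Physical, Emotional Well-being, Interference and Overall. The time frame for each is visit 5, and the derivation text names a score at that visit, for example "GH-INJ-CTB-Physical score at week 13 (visit 5"). Items are coded and scaled as follows: "0=Not at all, 1=A little, 2=Some, 3=A lot, 4=Extreme) normalised to a 0-100-point scale as" a domain-specific formula. SAP Section 4.6.1 gives the same single time point, and SAP Appendix 1 repeats the derivations.

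The unit column for these four rows points to footnote a. It reads "Negative score indicates that treatment burden is less compared to baseline" and appears under Protocol Table 9-2, under the SAP 4.6.1 table and under SAP Appendix 1.

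Protocol Section 8.1.5 limits the questionnaires: "The COAs should only be collected from participants switching to somapacitan from daily GH treatment". Section 6.1 places that switch at baseline. Section 2.3.2 expects that, for most participants, treatment in the study "most likely reduces the treatment burden compared to current available therapy as somapacitan is administered once weekly".

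**The concern.** The footnote and the derivation describe different quantities. The footnote presupposes a difference from a baseline value, with negative meaning improvement. The derivation gives one non-negative number per child, recorded after 13 weeks on somapacitan.

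What is at stake is how the result is read. The benefit section expects less burden than with existing therapy, and the questionnaire goes only to children who had been on daily injections. A reader of the tables who relies on the footnote will take the score to be a comparison with daily GH. The data as planned contain no such comparison, so any statement of reduced burden based on GH-INJ-CTB would be unsupported.

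**Working it through.** **Inputs.** The item coding (0 to 4), the three domain formulas and the rule for the overall score (mean of the three domains) come from Protocol Table 9-2 and are repeated in SAP Appendix 1.

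**Step 1: reproduce the stated 0-100 range.**
- "Physical (question 1-4): (Sum/16)*100": 4 items, sum 0 to 16. Minimum 0/16 × 100 = 0; maximum 16/16 × 100 = 100.
- "Emotional Well-being (question 5-10): (Sum/24)*100": questions 5 to 10 are 6 items, sum 0 to 24. Minimum 0; maximum 24/24 × 100 = 100.
- "Interference: (question 11-14): (Sum/16)*100": 4 items, sum 0 to 16. Minimum 0; maximum 100.
- Overall: the mean of three values between 0 and 100, so 0 to 100.

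The stated scale is reproduced.

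**Step 2: can a negative value occur?** The possible domain sums number 17, 25 and 17, giving 17 × 25 × 17 = 7,225 combinations. The overall score is negative in 0 of them, and no domain score can be negative.

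**Step 3: is there a baseline to compare with?** The time frame in both documents is visit 5 only. The questionnaire's row in the Section 1.2 flowchart carries a single mark. The flowchart columns are broken in the text available, so the visit number is taken from Table 9-2 and the SAP. Neither document defines a score at visit 2, a recalled score for daily GH, or a difference. Elsewhere in Table 9-2, change parameters are titled as changes and their derivations subtract the earlier value. The burden rows do neither. Planned within-child burden comparisons: 0.

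**Step 4: what would make the footnote true?** A change defined as week 13 minus visit 2 would range from 0 − 100 = −100 to 100 − 0 = +100 in each domain. For the Physical domain there are 17 × 17 = 289 possible pairs of sums, of which (289 − 17)/2 = 136 are negative. The footnote fits that quantity, but the plan does not derive it.

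**Side check.** Emotional Well-being is described as a sum of 4 items, but its question range covers 6 and its divisor is 24. Read literally as 4 items, the maximum would be 16/24 × 100 = 66.7. The score is non-negative either way, so the conclusion does not change, but the item count should be corrected in the same edit.

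**The case against.** The best defence is that the error is confined to one footnote. The derivations agree across both documents, the anchors fix the direction and range of the scale, and an absolute description of burden on weekly injections is a result in its own right. Burden appears in no objective, no hypothesis is tested, and the parameters are only summarised by indication. The statement in Section 2.3.2 is an expectation in a benefit-risk discussion, not something the study undertakes to demonstrate. All of this stands. It limits the consequence but does not reconcile the footnote with the derivation.

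A reader might go further and infer that no child can show any advantage over daily GH. That is too strong: GH-PPQ-Child, given to the same children at the same visit, records preference for previous treatment, current treatment or neither. It measures preference, not burden, but it is comparative.

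A reader might also infer that, under the footnote, every score from 0 to 100 counts as burden not reduced. The footnote does not say so. It assigns a meaning to negative values only, and no decision depends on the score.

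Finally, a visit 2 questionnaire comes too late for at least some children. The SAP is dated 24 June 2024 and says it was written after the first participant's first visit. The current protocol also provides up to 91 weeks beyond the 156-week period, ending by October 2027. If the full length is used, 156 + 91 = 247 weeks back from then puts the earliest baselines around the start of 2023. Enrolment status is not given. Nor is the questionnaire text, so its suitability for daily injections is not established. This objection also stands, and it makes the wording correction the main remedy.

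**Conclusion.** The footnote is wrong as written in all three places. It describes a change score that is not derived and a value that cannot occur (0 of 7,225 combinations). As planned, GH-INJ-CTB cannot show whether burden fell relative to daily GH, because each child contributes one post-switch score and no comparator.

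The consequence is limited to the interpretation and reporting of four other parameters. The primary safety endpoint and all secondary endpoints are untouched. The conclusion rests on the derivations in Table 9-2 and SAP Appendix 1 being those actually used, and on no baseline questionnaire being planned outside these documents. The number of switching children is not stated. With about ten completers planned per indication, it will be small in each sub-study.

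**What to change.** In Protocol Table 9-2, the SAP 4.6.1 table and SAP Appendix 1, replace footnote a on the four burden rows with: *0 to 100, higher means more burden; absolute score at week 13, no change from previous treatment is derived.* Report the scores descriptively, with no claim of reduced burden, and leave GH-PPQ-Child as the only previous-versus-current comparison. Correct the Emotional Well-being item count at the same time. This is a wording change only and can be made at any time before reporting.

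If any switching participants have not yet reached visit 2, also give them GH-INJ-CTB-Child there, before the first somapacitan dose and with reference to their daily injections, after confirming that the instrument is suitable for that use. Report week 13 minus visit 2 for those children separately from the absolute scores. The cost is about 3 minutes at an existing visit (the completion time in Protocol Table 8-1), a protocol and flowchart amendment, and a change score available for only part of the cohort.

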#### 4.6.2 Subgroup Analysis

Not applicable.

#### 4.7 Interim Analysis

Not applicable.

#### **4.8 Changes to Protocol-planned Analysis**

There are no changes to the protocol-planned analysis.

## 5 Sample size determination

No formal sample size calculation was performed in the four populations (SGA, TS, NS or ISS). The number of participants reflects what is expected feasible to enroll to provide adequate safety information in each indication.

Children above or equal to 10.0 years (girls with SGA, TS, NS and ISS) or 11.0 years (boys with SGA, NS and ISS) and below 18.0 years are not included in the pivotal study NN8640-4469. Based on a recommendation from the FDA, this age group will be investigated in study NN8640-4469.

Up to 50 participants are planned to be enrolled in this study. In total, at least 10 participants in each indication are planned to complete the study, as outlined below:

- **SGA:** Ten (10) female and male participants equal to or above 10.0 and 11.0 years, respectively, and below 18.0 years at screening.
- **TS:** Ten (10) female participants equal to or above 10.0 years and below 18.0 years at screening.
- **NS:** Ten (10) female and male participants equal to or above 10.0 and 11.0 years, respectively, and below 18.0 years at screening.
- **ISS:** Ten (10) female and male participants equal to or above 10.0 and 11.0 years, respectively, and below 18.0 years at screening.

## 6 Supporting Documentation

### 6.1 Appendix 1: Definition and calculation of endpoints, assessments and derivations

| Type                                   | Title                         | Time frame                                   | Unit               | Details   |
|--|-------------------------------|--|--------------------|---|
| Supportive secondary efficacy endpoint | Height velocity               | From baseline (week 0) to visit 7 (week 26). | cm/year            | Derived as:
HV at week 26 = (height at 26 weeks visit – height at baseline)/(time from baseline to 26 weeks visit in years).   |
| Supportive secondary efficacy endpoint | Change in Height SDS          | From baseline (week 0) to visit 7 (week 26). | Score b | Derived as the Height SDS value at baseline week 0 subtracted from the Height SDS value at week 26 (visit 7).
Height SDS is derived as:

$\text{Height SDS}_i = \frac{\left( \frac{\text{Height}_i}{\text{population median}} \right)^{\text{Skewness}} - 1}{\text{Skewness} * \text{population SD}}$
where i indicates the visit. The population median and standard deviation are the ones corresponding to the age at visit i. The population median and standard deviation and skewness are based on reference data.  |
| Supportive secondary efficacy endpoint | Change in Height Velocity SDS | From baseline (week 0) to visit 7 (week 26). | Score b | Derived as the Height Velocity SDS value at baseline week 0 subtracted from the Height Velocity SDS value at week 26 (visit 7). Height Velocity SDS is derived as:

$\text{HV SDS}_i = \frac{\text{HV}_i - \text{population mean HV}}{\text{population SD}}$
where i indicates the visit. The population mean and standard deviation corresponding to the age at visit i. The population mean and standard deviation are based on reference data.    |
| Supportive secondary efficacy endpoint | Change in IGF-I SDS           | From baseline (week 0) to visit 7 (week 26). | Score b | Derived as the IGF-I SDS value at baseline week 0 subtracted from the IGF-I SDS value at week 26 (visit 7). IGF-I SDS is derived as:

$\text{IGF - I SDS}_i = \frac{\left( \frac{\text{IGF - I}_i}{\text{population median}} \right)^{\text{Skewness}} - 1}{\text{Skewness} * \text{population SD}}$
where i indicates the visit. The population median and standard deviation are the ones corresponding to the age at visit i. The population median and standard deviation and skewness are based on reference data.      |
| Supportive secondary efficacy endpoint | Change in IGFBP-3 SDS         | From baseline (week 0) to visit 7 (week 26). | Score b | Derived as the IGFBP-3 SDS value at baseline week 0 subtracted from IGFBP-3 SDS value at week 26 (visit 7). IGFBP-3 SDS is derived as:

$\text{IGFBP - 3 SDS}_i = \frac{\left( \frac{\text{IGFBP - 3}_i}{\text{population median}} \right)^{\text{Skewness}} - 1}{\text{Skewness} * \text{population SD}}$
where i indicates the visit. The population median and standard deviation are the ones corresponding to the   |

|                 |  |   |                      |  |
|-----------------|--|---|----------------------|--|
|                 |  |   |                      | age at visit i. The population median and standard deviation and skewness are based on reference data.   |
| Other parameter | Child treatment burden measure: GH-INJ-CTB-Physical e                 | Visit 5   | Score a   | 
GH-INJ-CTB-Physical score at week 13 (visit 5).
 
GH-INJ-CTB – Physical score is derived as the sum of the 4 items (0=Not at all, 1=A little, 2=Some, 3=A lot, 4=Extreme) normalised to a 0-100-point scale as:
 
Physical (question 1-4): (Sum/16)*100
   |
| Other parameter | Child treatment burden measure: GH-INJ-CTB-Emotional Well-being e     | Visit 5   | Score a   | 
GH-INJ-CTB-Emotional Well-being score at week 13 (visit 5).
 
GH-INJ-CTB – Emotional Well-being score is derived as the sum of the 4 items (0=Not at all, 1=A little, 2=Some, 3=A lot, 4=Extreme) normalised to a 0-100-point scale as:
 
Emotional Well-being (question 5-10): (Sum/24)*100
  |
| Other parameter | Child treatment burden measure: GH-INJ-CTB-Interference e             | Visit 5   | Score a   | 
GH-INJ-CTB-Interference score at week 13 (visit 5).
 
GH-INJ-CTB – Interference score is derived as the sum of the 4 items (0=Not at all, 1=A little, 2=Some, 3=A lot, 4=Extreme) normalised to a 0-100-point scale as:
 
Interference: (question 11-14): (Sum/16)*100
  |
| Other parameter | Child treatment burden measure: GH-INJ-CTB-Overall treatment burden e | Visit 5   | Score a   | 
GH-INJ-CTB-Overall treatment burden score at week 13 (visit 5).
 
GH-INJ-CTB – Overall treatment burden score is derived as the mean of the GH-INJ-CTB – Physical score, GH-INJ-CTB- Emotional Well-being score and GH-INJ-CTB –Interference score.
  |
| Other parameter | Patient Preference: GH-PPQ-Child e                                    | Visit 5   | Categorical response | Patient Preference GH-PPQ-Child at week 13 (visit 5) (Previous treatment, Current treatment, No preference).   |
| Other parameter | Near adult height (NAH)  | 18 months prior to screening to visit 18 (week 156) | Yes/No               | Near adult height (NAH) will be derived. NAH is defined as HV < 2 cm/year calculated over a period of at least 9 months, males have reached a bone age of $\geq 16$ years and females has reached a bone age of $\geq 14$ years. If bone age is not available, then males have reached a chronological age of $\geq 17$ years and females have reached a chronological age of $\geq 15$ years. Historical height measurements collected at screening will be included in the derivation. |
| Other parameter | Change in height SDS at the visit when NAH is reached                            | From baseline (week 0) to the visit NAH is reached  | Score b   | Derived as the Height SDS value at baseline week 0 subtracted from the Height SDS value at the visit where NAH is reached.   |
| Other parameter | Midparental target height (MPH)  | Screening (visit 1)                                 | cm                   | 
Derived as:
 
Girls TH: (mother's height + father's height-13)/2.
 
Boys TH: (mother's height + 13 + father's height)/2.
  |
| Other parameter | MPH SDS  | Screening (visit 1)                                 | Score c   | 
MPH SDS is derived as:
 $\text{MPH SDS} = \frac{\text{Fathers height SDS} + \text{mothers height SDS}}{2}$   |

|                 |  |  |                    |  |
|-----------------|--|--|--------------------|--|
|                 |  |  |                    | Where parental height SDS is derived as:

$\text{Parental height SDS} = \frac{\text{Height} - \text{population mean}}{\text{population SD}}$

The population mean and standard deviation comes from reference data.    |
| Other parameter | Index of genetic height potential                                  | From baseline (week 0) to the visit NAH is reached | Score d | Derived as NAH SDS – MPH SDS   |
| Other parameter | Change in interventricular Septum end diastole (IVSed) SDS         | From baseline (week 0) to visit 7 (week 26)        | Score b | Derived as the IVSed SDS value at baseline week 0 subtracted from IVSed SDS value at week 26 (visit 7) for Turner syndrome.

IVSed SDS is derived as:

$\text{IVSed SDS}_i = \frac{\ln(\text{IVSed SDS})_i - \text{intercept} + \ln(\text{Weight}_i * \text{slope})}{\text{SD residual}}$

where i indicates the visit. The intercept, slope and SD residuals are the ones corresponding to the age at visit i. The intercept, slope and SD residuals are based on reference data.       |
| Other parameter | Change in left ventricle posterior wall end diastole (LVPWed) SDS  | From baseline (week 0) to visit 7 (week 26)        | Score b | Derived as the LVPWed SDS value at baseline week 0 subtracted from LVPWed SDS value at week 26 (visit 7) for Turner syndrome.

LVPWed SDS is derived as:

$\text{LVPWe SDS}_i = \frac{\ln(\text{LVPWe SDS})_i - \text{intercept} + \ln(\text{Weight}_i * \text{slope})}{\text{SD residual}}$

where i indicates the visit. The intercept, slope and SD residuals are the ones corresponding to the age at visit i. The intercept, slope and SD residuals are based on reference data.    |
| Other parameter | Change in left ventricle inner dimension end diastole (LVIDed) SDS | From baseline (week 0) to visit 7 (week 26)        | Score b | Derived as the LVIDed SDS value at baseline week 0 subtracted from LVIDed SDS value at week 26 (visit 7) for Turner syndrome.

LVIDed SDS is derived as:

$\text{LVIDed SDS}_i = \frac{\ln(\text{LVIDed SDS})_i - \text{intercept} + \ln(\text{Weight}_i * \text{slope})}{\text{SD residual}}$

where i indicates the visit. The intercept, slope and SD residuals are the ones corresponding to the age at visit i. The intercept, slope and SD residuals are based on reference data.  |
| Other parameter | Change in left ventricle inner dimension end systole (LVIDes) SDS  | From baseline (week 0) to visit 7 (week 26)        | Score b | Derived as the LVIDes SDS value at baseline week 0 subtracted from LVIDes SDS value at week 26 (visit 7) for Turner syndrome.

LVIDes SDS is derived as:   |

|                 |  |   |       |   |
|-----------------|--|---|-------|---|
|                 |  |   |       | $\text{LVIDes SDS}_i = \frac{\ln(\text{LVIDes SDS})_i - \text{intercept} + \ln(\text{Weight}_i * \text{slope})}{\text{SD residual}}$ 
where i indicates the visit. The intercept, slope and SD residuals are the ones corresponding to the age at visit i. The intercept, slope and SD residuals are based on reference data.
   |
| Other parameter | Change in sitting height/height (SH/H)         | From baseline (week 0) to visit 7 (week 26)   | Ratio | Derived as SH/H at baseline week 0 subtracted from SH/H at week 26 (visit 7) for TS & ISS .  |
| Other parameter | Change in sitting height/height SDS (SH/H SDS) | From baseline (week 0) to visit 7 (week 26)   | Ratio | 
Derived as SH/H SDS at baseline week 0 subtracted from SH/H SDS at week 26 (visit 7) for TS & ISS.
 
SH/H SDS is derived as:
 $\text{SH/H SDS}_i = \frac{\left( \frac{\text{SH/H}_i}{\text{population median}} \right)^{\text{Skewness}} - 1}{\text{Skewness} * \text{population SD}}$ 
where i indicates the visit. The population median and standard deviation are the ones corresponding to the age at visit i.
 |
| Other parameter | Change in bone age/chronological age           | From screening (visit 1) to visit 9 (week 52) | Ratio | The bone age/chronological age value at screening (visit 1) subtracted from the bone age/chronological age value at week 52 (visit 9).  |

aNegative score indicates that treatment burden is less compared to baseline.

bPositive score indicates that the value is closer to or above the reference population compared to baseline.

cNegative values indicate that the values are lower than the reference population.

dNegative values indicate that the NAH is below the genetic height potential.

eOnly to be collected from participants switching to somapacitan from daily GH treatment.

